5.3. STUDY PROCEDURE RISKS

Risks of 68Ga-PSMA PET

The PET tracer, 68Ga-PSMA, is a PSMA ligand radiolabelled with 68Ga to enable its use for PET imaging. Several preclinical and clinical studies have shown the safety of 68Ga-PSMA. The critical dose-organs are the kidneys (0.16 mSv/MBq). Based on the FDA, a single-organ dose of 0.05 Sv is allowed. This corresponds to an activity of 289.9 – 414 MBq (7 – 11 mCi) of 68Ga-PSMA for a 70-100 kg male patient with a prostate cancer. Accordingly, the effective dose expected to the whole body is 0.01 Sv, which is below the 0.03 Sv upper limit recommended by the FDA (DeGrado et al., JNM 43,1:92-96, 2002). No adverse effects due to intravenous administration of 68Ga-PSMA for imaging have been reported in the published literature. Overall, 68Ga-PSMA PET SCAN may be used in clinical research with no risk to patients with prostate cancer.

Risks of ferumoxtran-10, Combidex® Nano MRL:

A single death during infusion of Combidex has been reported in the United States. This was associated with rapid infusion of the agent without a rate-limiting IV micro-filter in a patient with pre-existing cardiac morbidity. There is a known risk of hypersensitivity, anaphylaxis and cardiac compromise associated with the IV infusion of iron or dextran products. Manufacturer recommendations stipulate that Combidex must be administered by a slow IV-infusion through a micro-filter over at least 30 minutes. To date over 200 patients have undergone Combidex scanning at Radboud UMC, with only 2 patients experiencing any issues – one patient experienced dizziness/light-headedness which was relieved by stopping the infusion for several minutes. The other patient developed a mild cellulitis at the injection site. Currently a larger study in Russia is underway recruiting over 400 patients. Many of these have already undergone Combidex scanning, adding to the safety data using the prescribed infusion protocol. During this trial patient safety will be ensured during infusion through the following steps:

Medical investigators, the radiologists and a radiology technician will travel to Nijmegen to personally learn the safe injection technique of Combidex from [name], as well as the reading of the Nano MRL. They will also convey this information to other members who have responsibility for reading the Nano MRL as well as its administration at St Vincent's Hospital.

This will be done at the The Kinghorn Cancer Centre (a facility of the St Vincent's Hospital) with a full anaphylaxis and resuscitation kit at the bedside, as well as an anaesthetist who is present in the hospital being on standby for emergencies. The intensive care staff will also be advised of the trial and will be notified in advance each day that patients are having an infusion, with a team member on standby by phone in the case of emergency. These extra-ordinary precautions will hopefully ensure that any adverse event during infusion is rapidly dealt with and controlled with minimal risk to patients. Should adverse reactions be noted at anytime throughout the procedure, the infusion will be stopped immediately and the St Vincent's Hospital IV Contrast Allergy Protocol will be referred to.

Upon the completion of Combix infusion, each patient will be required to remain at St. Vincent's Hospital for at least one hour.

5.4. RECRUITMENT AND SCREENING

Participants have been referred to an urologist for a radical prostatectomy and lymph node dissection following a diagnosis of prostate cancer. The participant will be intermediate and high-risk cancer patients with a $\geq 10\%$ probability on LN where LND would currently be performed as part of the treatment protocol (guided by the updated Briganti nomogram) [34].

The participant will provide the following information as part of the referral and for assessment to participate:

- 99mTc bone scan and MRI scan of abdomen and pelvis
- Documentation of demographic variables
- Pre-prostatectomy PSA, clinical stage, grade
- Use of hormones or other therapies prior to prostatectomy

The urologist will then assess the participant for enrolment into the trial based on the inclusion and exclusion criteria. Should the participant meets the inclusion criteria and none of the exclusion criteria, the participant will be referred to the St Vincent's Nuclear Medicine Department for recruitment into the trial.

5.5. INFORMED CONSENT PROCESS

The St Vincent's Prostate Cancer Centre will provide details of the trial and will provide the participant with the Participant Information Statement and Consent Form. If the participant wishes to participate, written consent will be requested from the participant by a member of the research team

5.6. ENROLMENT PROCEDURE

The potential participant will be identified by the urologist for prostate cancer surgery. The urologist will assess the potential participant using the inclusion and exclusion selection criteria. If the participant is eligible, consent will be sought. Following participant consent, a unique study will be provided to the participant in place of any identifiable information. An initial assessment form (Form A) will be completed to collect demographic and clinical information.

6. SAFETY

6.1. ADVERSE EVENT REPORTING

An adverse event to either 68Ga-PSMA PET Scan and/or Nano MRL will be considered as any unfavourable and unintended sign, symptom, or disease temporally associated with their use, whether or not they are directly related to the 68Ga-PSMA PET Scan and/or Nano MRL. Should an adverse event occur, it will be reported to the trial investigators, as well as documented in the participant's medical records.

6.2. SERIOUS ADVERSE EVENT REPORTING

A serious adverse event (SAE) is defined as:

For medicines, also referred to as serious adverse drug reaction, any untoward medical occurrence that at any dose:

- results in death;
- is life-threatening;
- requires in-patient hospitalisation or prolongation of existing hospitalisation;
- results in persistent or significant disability/incapacity;
- is a congenital anomaly/birth defect; or
- is a medically important event or reaction.

NOTE: The term 'life-threatening' in the definition of 'serious' refers to an event in which the patient was at risk of death at the time of the event; it does not refer to an event/reaction which hypothetically might have caused death if it were more severe.

In the result of a serious adverse event, it will be reported to the St Vincent’s HREC, documented in the participant’s medical record and presented to the Data Safety and Monitoring Board.

6.3. DATA SAFETY AND MONITORING BOARD

A data safety and monitoring board will be created to review any safety concerns arising from the trial. It will consist of investigators from St Vincent’s Hospital Sydney, the St Vincent’s Prostate Cancer Centre, the Wesley Hospital, Brisbane and Radboud University Nijmegen, the Netherlands and a two nominated independent observers.

6.4. EARLY TERMINATION

The trial may end early if the welfare of participants is at risk. Participants will be informed in this situation.

7. STATISTICAL CONSIDERATIONS

a) Trial Size:

We will now recruit 120 patients (60 from St Vincent’s Hospital, Sydney and 60 from the Wesley Hospital, Brisbane) from the originally planned 80 patients. Based on the previous calculation, that each of the 80 patients will have 6 packets (a lump of fat containing lymph nodes) on average, we will be comparing 480 packets in total. This number will give 90% power to detect a 10% or less discordance between final histology analysis and the combined imaging modalities consensus. Sample size was calculated based on agreement of combination of both images together with histology. We used 15% as the probability of positive lymph node from histology results, based on literature the probability of positive lymph node result from histology is between 11% and 17% [35].

For 95% sensitivity and 90% specificity of combination of the two images, we need to test 178 packets. To achieve this number of packets we need to recruit a maximum of 32 patients. To account for correlation between packets from each patient, we have considered high effect size of equal to 2.5 which results in the requirement of 80 patients. The new recruitment target will exceed this requirement.

Statistical calculations for the MAGNIFI trial sample size are set out below:

The data for N patients, with n packets per patient, will be tabulated as follows:

| Combined Test | Histology | | Total |
|---------------|-----------|----------|-------|
| | Positive | Negative | |
| Positive | A | B | A+B |

| | | | |
|----------|-----|-----|-----|
| Negative | C | D | C+D |
| Total | A+C | B+D | N×n |

To take account of clustering, a variance inflation factor VIF is calculated as follows:

$$VIF = 1 + (n-1)\rho$$

where n is the number of packets per patient (6) and ρ is the intra-class correlation, a measure of clustering within patients (assumed to be a maximum of 0.3). This yields a VIF of 2.5.

The formula for the sample size for a two sided McNemar test, taking into account the VIF, is then (based on reversing equation (5) of Gönen, 2004):

$$N = \frac{(z_{1-\alpha/2}\phi + z_{1-\beta}\sqrt{\phi^2 - 0.25\delta^2(\phi + 3)})^2}{n\phi\delta^2/(1 + (n\phi - 1)\rho)}$$

where:

z is a percentile from the standard normal distribution

α is the level of significance (two-sided test, α = 0.05)

1-β is the power (assumed to be 0.90)

φ is the total proportion of discordant pairs: (B+C)/ (N×n) in above table

δ is the difference in the proportions of the two types of discordant pairs: (B-C)/ (N×n)

n = number of observations per patient (6)

For the calculations, it was additionally assumed that the proportion of positive packets was 0.15, φ = 0.10, and δ = 0.04. This assumes the following proportions:

[figure not shown]
| Combined Test | Histology | | Total |
|---------------|-----------|----------|-----------|
| | Positive | Negative | |
| Positive | 0.12 | 0.07 | 0.19 |
| Negative | 0.03 | 0.78 | 0.81 |
| Total | 0.15 | 0.85 | N×n = 480 |

Gonen M. Sample size and power for McNemar's test with clustered data. *Statistics in Medicine* 2004, 23: 2283-2294

b) Statistical Analysis:

We will compare 'packet concordance rate' between histology and MR Lymphography using a MRA arterial map (that can be acquired at the MRL) to locate the position of the lymph node, the 68Ga PSMA PET SCAN plus a combined evaluation, and histology. As indicated in the diagram below, lymph nodes are removed by one lump of fat (region-packet) at a time (refer to region-packets 'a' to 'f' in figure below). The two tests (MR lymphography and 68Ga PSMA PET) will indicate (with error)

whether each node is positive or not, and thus whether each region-packet is positive (at least one node positive) or not (no nodes positive). The combined evaluation is a consensus of the two tests: region-packets are positive if one or both tests indicate positive and negative only if both tests indicate the region-packet is negative. Using histology, we can assess the accuracy of the two tests (plus combined evaluation) in terms of false positives.

| | Histology | MR Lymphography | Ga68 PSMA | Imaging Consensus |
|---|-----------|-----------------|-----------|-------------------|
| a | Negative | Negative | Negative | Negative |
| b | Positive | Positive | Positive | Positive |
| c | Negative | Positive | Positive | Positive |
| d | Negative | Negative | Negative | Negative |
| e | Positive | Positive | Positive | Positive |
| f | Positive | Negative | Negative | Negative |

We will calculate the CONCORDANCE rate for positive nodes in each packet with their corresponding region on imaging, both against each individual imaging modality and against a summed score from both imaging techniques. Sensitivity, specificity, negative predictive values (NPVs), and positive predictive values (PPVs) will be reported [31, 32]. The maximum likelihood estimates (MLEs) of PPV and NPV will be calculated from the MLEs of the sensitivity, specificity, and prevalence rate. Hierarchical modelling will be used to test for concordance between matched results from each packet.

Secondary outcome of interest is quality of life and the complications. As part of initial longitudinal analyses quality of life (as measured using EORTC-QLQ-C30) will be evaluated using one-way ANOVA. To examine differences in quality of life scores between the two groups (standard eLND versus super-eLND), baseline characteristics will be compared between groups to assess whether the groups are balanced using Chi-square tests and Fisher's exact tests. The additional analysis involves comparing the change in quality of life scores (worsened, stable or improved quality of life) from baseline to 2 and 6 months between the groups using Chi-square tests and Fisher's exact tests. Similar method will be used evaluating the differences in the complication score.

c) Interim Analysis:

An analysis of the data will be performed after every 10 patients have completed imaging and pelvic lymph node dissection. This will allow the trial statistician and data monitoring committee to identify any problems or discrepancies with data collection and recording, in addition to identifying any possible technical issues that might jeopardise

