2. STUDY OBJECTIVES

Hypothesis:

THE ADVANTAGES OF ACCURATE NODAL IMAGING FOR PATIENTS WITH INTERMEDIATE AND HIGH-RISK PROSTATE CANCER:

- (i) If combined anatomical and functional nodal assessment is negative, then patients do not need a node dissection.
- (ii) If combined anatomical and functional nodal assessment is positive, then appropriate treatment to the nodes (in conjunction with treatment to the primary cancer) can be planned. This may involve:
 - (a) Anatomically targeted node dissection (in place of e-LND)
 - (b) Anatomically targeted radiotherapy dose-painting
 - (c) The use of systemic chemotherapy (multiple small nodes in many locations) followed by the use of hormonal treatment (protocols analogous to those used in breast cancer oncology).
- (iii) This multi-modal approach will decrease the failure rate of current treatment protocols where nodal status is unknown and standard nodal fields are irradiated or dissected based on probability.

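### The stated 10% discordance target pools both error types, is not what the McNemar calculation tests, and rests on two contradictory sets of planning accuracy

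*Protocol*

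**What the plan says.** Section 7a of the protocol states: "This number will give 90% power to detect a 10% or less discordance between final histology analysis and the combined imaging modalities consensus". There the sentence refers to 480 packets from 80 patients. The synopsis repeats it for 720 packets from 120 patients. No other performance target for the combined imaging appears in the protocol.

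The calculation beneath it is a two-sided clustered McNemar test at 5% significance and 90% power. Total discordance φ is defined as (B+C)/(N×n) and δ as (B−C)/(N×n), where B is false-positive and C false-negative packets. The inputs are "the proportion of positive packets was 0.15, φ = 0.10, and δ = 0.04", and a 2x2 table of proportions follows from them.

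The text of the same section gives a different basis: "For 95% sensitivity and 90% specificity of combination of the two images, we need to test 178 packets". On prevalence it says "We used 15% as the probability of positive lymph node from histology results" and cites a literature range of 11% to 17%.

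Sections 5.2 (Histopathology) and 7b plan to report sensitivity, specificity, PPV and NPV, with no value attached to any of them. Hypothesis (i) in Section 2 reads: "If combined anatomical and functional nodal assessment is negative, then patients do not need a node dissection".

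**The concern.** Overall discordance counts an imaging-positive, histology-negative packet the same as a missed metastatic packet. With 85% of packets assumed negative, the sum depends heavily on specificity and can stay at or below 10% over a wide range of sensitivity. Omitting dissection after negative imaging depends on the false negatives alone. A report that discordance was 10% or less, taken as the headline result, would leave that question open.

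Two further features make the target unreliable as written. The power sentence describes something that the McNemar calculation does not test. And the section carries two incompatible assumptions about how good the combined test is, so it is unclear what performance the trial was sized for.

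**Working it through.** **Inputs (all from Section 7a).** Packet prevalence 0.15 (cited range 0.11 to 0.17); φ = 0.10; δ = 0.04; n = 6 packets per patient; ρ = 0.3, so VIF = 1 + 5 × 0.3 = 2.5; two-sided α = 0.05; power 0.90; table cells 0.12, 0.07, 0.03, 0.78; text accuracy 95%/90%.

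**1. The plan's own figure.** Put into the formula as printed, these give

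- numerator: (1.960 × 0.10 + 1.2816 × √(0.01 − 0.25 × 0.0016 × 3.10))² = 0.0998
- denominator: 6 × 0.10 × 0.0016 / (1 + (0.6 − 1) × 0.3) = 0.00096/0.88 = 0.001091
- N = 0.0998/0.001091 = 91.5, so 92 patients.

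The stated 80 is not reproduced; it arises as 32 × 2.5. That is a separate matter, and nothing below depends on it.

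**2. What is tested.** The McNemar null hypothesis is B = C, that is δ = 0. The value φ = 0.10 is assumed, not tested. Imaging with B = C = 0.05 has exactly 10% discordance and a sensitivity of 0.10/0.15 = 67%, and it satisfies the null. Rejecting the null shows that one kind of error is more frequent than the other. It says nothing about whether B+C is at or below 10%.

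**3. What 10% discordance implies for sensitivity.** Discordance = prev × (1 − sens) + (1 − prev) × (1 − spec). Setting this to 0.10 at prevalence 0.15:

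sens = 1 − [0.10 − 0.85 × (1 − spec)]/0.15

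| Specificity | Sensitivity at 10% discordance |
|---|---|
| 90% | 90% |
| 91.8% | 80% |
| 95% | 62% |
| 97% | 50% |
| 99% | 39% |
| 100% | 33% |

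Sensitivity of 50% corresponds to specificity 1 − (0.10 − 0.075)/0.85 = 97.1%, so more than half of positive packets can be missed only above that specificity. At 100% specificity the sensitivity is 1 − 0.10/prev: 9% at prevalence 0.11 and 41% at 0.17.

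**4. The two planning assumptions, at 15% prevalence.**

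| | Text of 7a | Table in 7a |
|---|---|---|
| Sensitivity | 95% | 0.12/0.15 = 80% |
| Specificity | 90% | 0.78/0.85 = 91.8% |
| B | 0.85 × 0.10 = 0.085 | 0.07 |
| C | 0.15 × 0.05 = 0.0075 | 0.03 |
| φ = B+C | 9.25% | 10.0% |
| δ = B−C | 7.75% | 4% |
| NPV | 0.765/0.7725 = 99.0% | 0.78/0.81 = 96.3% |

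The missed proportion differs by 0.03/0.0075 = 4. Among 720 × 0.15 = 108 positive packets that is about 5 against 22 missed, while overall discordance differs by 0.75 points.

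**5. Precision with 120 patients.** With 108 positive packets and 95% sensitivity, the half-width is 1.96 × √(0.95 × 0.05/108) = 4.1 points at VIF 1 and 4.1 × √2.5 = 6.5 points at VIF 2.5.

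**The case against.** The 10% is part of a power statement, not a decision rule. The protocol nowhere says that observed discordance at or below 10% counts as success, or that it would justify omitting dissection. Hypothesis (i) is set out as an advantage of accurate nodal imaging. Sensitivity and NPV will be reported in any case, and thresholds may properly sit in an analysis plan that is not shown. All of this stands. The point is not that a threshold is missing. It is that the target the protocol does state pools the errors, and that the calculation cited for it tests something else.

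A reader might infer that the trial would declare success for imaging that misses most metastatic packets. The documents do not support that. Missing more than half needs specificity above about 97%, whereas the protocol plans 90% to 92%, at which 10% discordance corresponds to 80% to 90% sensitivity. The consensus rule in Section 7b, which calls a packet positive if either test is positive, also favours sensitivity at the expense of specificity.

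The McNemar test would not treat such imaging like the planned imaging either. With 720/2.5 = 288 effective packets, z = (B−C) × √288/√(B+C). For 50% sensitivity and 99% specificity, B = 0.0085 and C = 0.075, so z = −3.9. For 95%/90%, z = +4.3. The opposite signs would reveal under-calling. But both results are significant, so a significant test is not evidence of adequate accuracy.

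**Conclusion.** The point holds in a limited form. The only stated performance target mixes two errors with different consequences, and the cited calculation gives no power to show it. At 15% prevalence, 10% discordance is compatible with sensitivity from about 90% (specificity 90%) down to 33% (specificity 100%). The lower part of that range is possible under the target but is not what the protocol expects. The target therefore cannot by itself support hypothesis (i).

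The contradiction in planning accuracy needs no assumption beyond the protocol's own 15% prevalence: 95%/90% and the printed table cannot both describe the combined test. The results are per packet. Hypothesis (i) concerns whole patients, and the conversion depends on how positive packets cluster, which the protocol does not give.

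**What to change.** In Section 7a and the synopsis:

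- Restate the target for the combined test as packet-level sensitivity and specificity, each with a cluster-adjusted confidence interval. Keep overall concordance as a descriptive result.
- State the precision that 120 patients give: about 108 positive packets, so 95% sensitivity to within 4.1 to 6.5 points for VIF 1 to 2.5.
- Make the stated accuracy, the table, φ and δ agree. For 95%/90% the cells are 0.1425 (true positive), 0.085 (false positive), 0.0075 (false negative) and 0.765 (true negative), with φ = 0.0925 and δ = 0.0775. Alternatively, correct the stated accuracy to the table's 80% and 91.8%.

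Any minimum acceptable sensitivity is for the sponsor to set.

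The cost is mainly wording: the trial already plans to calculate these measures, and no new data are needed. Changing φ and δ means rerunning the sample-size calculation. If the sponsor adds a formal minimum for sensitivity or specificity, that criterion needs its own power calculation.

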2.2. SECONDARY OBJECTIVES

Determine whether concordance of these two imaging technologies (68Ga-PSMA PET - functional imaging, and Nano MR - anatomical imaging) is worse, better or equal to lymph-node dissection.

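### The 90% power claim for discordance of 10% or less is not what the printed McNemar calculation powers

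*Protocol*

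**What the plan says.** Section 7 a) of the Protocol, after counting 80 patients × 6 = 480 packets, states: "This number will give 90% power to detect a 10% or less discordance between final histology analysis and the combined imaging modalities consensus". The Synopsis (Statistical Analyses) repeats the sentence for 120 patients × 6 = 720 packets.

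The derivation in Section 7 a) is introduced with "The formula for the sample size for a two sided McNemar test, taking into account the VIF, is then". It sets two-sided α = 0.05 and power 0.90, and defines two parameters from the imaging-by-histology table:

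- "φ is the total proportion of discordant pairs", that is (B+C)/(N×n), set at 0.10.
- "δ is the difference in the proportions of the two types of discordant pairs", that is (B−C)/(N×n), set at 0.04.

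B is imaging positive with histology negative; C is imaging negative with histology positive. The planning table has B = 0.07, C = 0.03 and 15% of packets positive.

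The primary objective (Section 2.1) compares imaging with histology as gold standard. The secondary objective (Section 2.2) asks whether the two imaging methods together are, in the Protocol's words, "is worse, better or equal to lymph-node dissection". Hypothesis (i) in Section 2 is that a negative combined assessment makes node dissection unnecessary. Section 7 b) plans concordance rates, sensitivity, specificity, PPV, NPV and a hierarchical model. It does not mention McNemar.

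**The concern.** McNemar's null hypothesis is B = C: imaging and histology call the same share of packets positive. Its power depends on B−C. The total B+C enters the formula only as a quantity that must be guessed in advance, and no maximum discordance is stated or tested. Power to detect discordance of 10% or less is therefore not a property of this calculation.

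With histology as the reference, rejecting B = C shows only that imaging over-calls or under-calls. Failing to reject does not show agreement. Whether negative imaging can spare a dissection turns on sensitivity and NPV, which the test does not address. A reader of the Synopsis would believe that the trial has 90% power on a question for which no power was calculated.

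**Working it through.** **Inputs (Protocol, Section 7 a).** φ = 0.10; δ = 0.04; n = 6; ρ = 0.3; z = 1.960 (two-sided 5%) and 1.2816 (90% power); 15% of packets positive. N = 80 or 120 patients.

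**1. The plan's own figure.** The printed formula is N = [z(α)·φ + z(β)·√(φ² − 0.25δ²(φ+3))]² ÷ [nφδ²/D], with D = 1 + (nφ−1)ρ.

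- D = 1 + (0.6−1)×0.3 = 0.88
- Square root: √(0.01 − 0.25×0.0016×3.1) = 0.09359
- Numerator: (0.19600 + 0.11995)² = 0.09982
- Denominator: 6×0.10×0.0016/0.88 = 0.001091
- N = 91.5, so 92 patients, not 80

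Solved for power: z = [√(N·nφδ²/D) − 1.960φ] ÷ √(φ² − 0.25δ²(φ+3)).

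- 80 patients: (0.2954 − 0.1960)/0.09359 = 1.06, power 85.6%
- 120 patients: (0.3618 − 0.1960)/0.09359 = 1.77, power 96.2%

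So 90% at 80 patients is not reproduced from the stated inputs. Section 7 a) also gives a VIF of 2.5, whereas the printed D is 0.88. With D = 2.5 the formula gives 260 patients, with power 41% at 80 and 58% at 120. These are separate faults. They are noted because the conclusion below holds with either factor.

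**2. Hold discordance at 10% and vary the split** (120 patients).

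| B / C | B+C | δ | Sensitivity 1−C/0.15 | Specificity 1−B/0.85 | Power, D = 0.88 | Power, D = 2.5 |
|---|---|---|---|---|---|---|
| 0.07 / 0.03 | 0.10 | 0.04 | 80% | 92% | 96% | 58% |
| 0.055 / 0.045 | 0.10 | 0.01 | 70% | 94% | 14% | 8% |
| 0.05 / 0.05 | 0.10 | 0 | 67% | 94% | 5% (= α) | 5% |

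For the second row, D = 0.88: (0.0905 − 0.1960)/0.0996 = −1.06, power 14%. Discordance is identical in all rows, so the power figure cannot describe discordance.

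**3. What 720 packets give on the planned measures.** At 15% positive there are 108 positive and 612 negative packets. Dividing by 2.5 as a conservative bound gives effective sizes m = 43.2 and 244.8. For NPV the planning table has 0.81×720 = 583 imaging-negative packets, so m = 233. For total discordance, m = 720/2.5 = 288. The Wilson 95% interval is [p + z²/2m ± z√(p(1−p)/m + z²/4m²)] ÷ (1 + z²/m).

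| Quantity | Assumed value | Interval |
|---|---|---|
| Sensitivity | 80% | 66–89% |
| Sensitivity | 95% | 84–99% |
| Specificity | 92% | 88–95% |
| NPV (0.78/0.81) | 96% | 93–98% |
| Total discordance | 10% | 7–14% |

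The Wald interval is unsuitable near 1: for 95% sensitivity the half-width is 1.96√(0.95×0.05/43.2) = 6.5 points, which puts the upper limit at 101.5%.

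The factor 2.5 presumes six packets per cluster, but positive packets average 108/120 = 0.9 per patient. If ρ = 0.3 applies both to positivity and to reading error (an assumption), a positive packet has on average 5×(0.15 + 0.3×0.85) = 2.0 other positives in the same patient. The factor is then 1 + 2.0×0.3 = 1.6, m is 108/1.6 = 67.5, and the sensitivity intervals become 69–88% (at 80%) and 87–98% (at 95%).

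**4. What a test of discordance would look like** (illustration: maximum 10%, one-sided 2.5%, VIF 2.5). With 720 packets, power is 38% if true discordance is 7% and 88% if it is 5%. If true discordance equals the maximum, power is 2.5% at any size.

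**The case against.** Four points can be made for the plan.

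- **No McNemar verdict is planned.** A reader might infer that the trial could rank worse imaging above better. At 95% sensitivity and 90% specificity (B = 61.2, C = 5.4 of 720; discordance 66.6/720 = 9.25%), McNemar's chi-square is 55.8²/66.6 = 46.8, or 18.7 after dividing by 2.5. Imaging with B = C = 36 (67% sensitivity, 94% specificity) gives zero. But Section 7 b) would report that imaging as 67% sensitive, and no rule reads non-significance as equality. The Protocol does not support the stronger inference. It remains a risk only if someone later read the result that way.
- **There is a second route to 80 patients.** Section 7 a) also starts from 95% sensitivity and 90% specificity: 178 packets, at most 32 patients, and 32×2.5 = 80. The size is therefore not justified by McNemar alone. This stands, but the basis of the 178 is not shown and this route does not support the power sentence either.
- **McNemar fits one reading of objective 2.** Whether imaging calls more or fewer packets positive than dissection is a literal sense of worse or better, so it goes too far to say that the trial never asks the question. It is still not discordance.
- **Detail may sit in the SAP.** The interval method and acceptance limits can be left there. A wrong power statement in the Protocol cannot be excused on that ground.

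**Conclusion.** The point holds as a wrong statement in the Synopsis and Section 7 a). The printed calculation powers a test of B = C at a difference of 0.04. It gives no power for total discordance, sensitivity or NPV. With discordance fixed at 10% and 120 patients, power runs from 96% to 14% on the split of errors alone (58% to 8% with VIF 2.5). Going from 80 to 120 patients does not cure this, because more packets only sharpen the test of B = C.

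The planned estimates are sound in kind and the data needed are already collected, so the trial is not shown to be too small or its analysis invalid. The precision figures rest on 15% positive packets, six packets per patient and ρ of at most 0.3. The sensitivity intervals depend most on the clustering factor.

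**What to change.** 1. Delete the discordance power sentence from the Synopsis and Section 7 a).
2. Justify 120 patients by the expected precision of packet-level sensitivity, specificity and NPV of the combined read against histology. Use patient-clustered intervals suited to proportions near 1 (Wilson or model-based, not Wald) and a design factor computed for the relevant subset of packets. The intervals at VIF 2.5 above can serve as a conservative bound.
3. If a power statement on discordance is wanted, state a maximum, test total discordance one-sided against it, and give the power at a stated true value below that maximum.
4. State in objective 2 that equality will not be inferred from a non-significant test.

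The cost is Protocol wording only: no extra patients or data. The price is that a 90% power figure gives way to a less favourable precision statement. Since Section 7 c) has the data analysed after every 10 patients, any maximum or minimum added now should be recorded with its date and with what its authors had seen.
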